# 12.8. Appendix 8: Values of Potential Clinical Importance

# 12.8.1. Laboratory Values

Element	Reporting Detail
Laboratory Values and Adverse	The central laboratory will flag lab parameter toxicities directly in the provided datasets based on Division of AIDS Table for Grading the Severity of Adult and Paediatric Adverse Events Version 2.1, March 2017
Events	

## 12.8.2. ECG

ECG values of potential clinical importance are defined as QTc > 500 msec or increase from baseline in QTc  $\geq$  60 msec.

## 12.9. Appendix 9: Snapshot Algorithm Details

### **Detailed Algorithm Steps**

- Consider an analysis visit window for Month X as defined in Table 8 and Table 9.
- The HIV1-RNA threshold of 50, copies/mL will be analysed, in this study
- The analysis window 'Month 12' and HIV1-RNA threshold of '50 copies/mL' are used for the purpose of illustration. A subject's Snapshot response and reason at Month 12 are categorized as below.
  - HIV1-RNA < **50** copies/mL
  - o HIV1-RNA ≥ **50** copies/mL

Data in window not below 50
Discontinued for lack of efficacy
Discontinued for other reason while not below 50
Change in background therapy\*

Discontinued study for other reasons
On study but missing data in window

 The steps in determining response and reasons are indicated in Table below, in the order stated.

#### **Detailed steps**

Please note that the following scenarios will NOT be penalized Per Snapshot algorithm (i.e. please exclude these scenarios from **Condition** 1-4).

 Dose reduction, dropping a component, or change in formulation (e.g. 'Tivicay + Kivexa' to 'Triumeq' with the identical ingredients)

Condition ('Month 12' indicates Month 12 window)	Response	Reasons
If non-permitted change in background therapy prior to Month 12	HIV1-RNA ≥ 50	Change in background therapy
2. If permitted change [a] in background therapy prior to Month 12 AND the latest on-treatment VL prior to/on the date of change is ≥ 50 c/m (NA to this study)	HIV1-RNA ≥ 50	Change in background therapy
3: If non-permitted change in background therapy		

\* Note: since changes in ART are not permitted in this protocol, all such subjects who change ART during the maintenance phase and prior to an analysis timepoint will be considered 'HIV1-RNA ≥ **50** copies/mL'. Participants with protocol permitted oral bridging treatment will not be considered 'HIV-1 RNA ≥ 50 c/mL' due to 'change in ART'.

during	Month 12		
	Last on-treatment VL during Month 12 prior to/on the date of change ≥ 50 c/mL	HIV1-RNA ≥ 50	Data in window not below 50
	Last on-treatment VL during Month 12 prior to/on the date of change <50 c/mL	HIV1-RNA < 50	
	No VL during Month 12 prior to/on the date of change	HIV1-RNA ≥ 50	Change in background therapy
Month 1	mitted change [a] in background therapy during 2 AND the last on-treatment VL prior to/on the change is ≥ 50 c/mL (NA to this study)		
4.1	this last on-treatment VL occurs prior to Month 12	HIV1-RNA ≥ 50	Change in background therapy
	this last on-treatment VL occurs during Month 12 but prior to/on the date of change	HIV1-RNA ≥ 50	Data in window not below 50
5: If non	e of the above conditions met		
5.1	VL available during Month 12		
	Last on-treatment VL during Month 12 ≥ 50 c/mL	HIV1-RNA ≥ 50	Data in window not below 50
	
 
Last on-treatment VL during Month 12 <50 c/mL
 
	HIV1-RNA < 50	
5.2	No VL during Month 12		
permane participa and the to the fo CAB LA Min (ma	subjects still on study i.e. a participant has not ently discontinued the study treatment yet, or if a ant permanently discontinued the study treatment upper bound of analysis snapshot window is prior llowing date:  + RPV LA arm: x(Date of last CAB LA + RPV LA injection + 67, last Dose of Oral CAB + RPV + 1), withdrawal date)	No virologic data at Month 12 Window	On study but missing data in window
	RPV arm: te of Last oral dose of DTG + RPV + 1, withdrawal		
where 'V	Vithdrawal Date' refers to the date the participant		

failed to complete per corresponding conclusion form.		

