6.7. Dose Modifications

No dose reductions, modifications, or changes in the frequency of any components of each regimen will be allowed during the study beyond what is allowed within the protocol or directly approved by the study Medical Monitor. Protocol waivers or exemptions are not allowed. Therefore, adherence to the study design requirements is essential and required for study conduct. See Section 4.4 for the justification of dose.

Supplementary study conduct information not mandated to be present in this protocol is provided in the accompanying Study Procedures Manual (SPM), which is available on the online Study Web Portal. The SPM will provide the site personnel with administrative and detailed technical information.

Please refer to [Appendix 10](#) in Section 12.10 for study management information during the COVID-19 pandemic.

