7. DISCONTINUATION OF STUDY INTERVENTION AND PARTICIPANT DISCONTINUATION/WITHDRAWAL

A participant may withdraw consent and discontinue participation in this study at any time at his/her own request. The investigator may also, at his or her discretion, discontinue the participant from participating in this study at any time (e.g., safety, behavioral or administrative reasons). If a participant withdraws from the study, he/she may request destruction of any samples taken, and the investigator must document this in the site study records. Withdrawn participants will not be replaced.

All participants who discontinue prematurely from the study, irrespective of arm, will be asked for additional information to establish the reason for withdrawal.

Participants are not obligated to state the reason for withdrawal. However, the reasons for withdrawal, or failure to provide a reason, must be documented by the Investigator on the Completion/Withdrawal section of the electronic case report form (eCRF). Every effort should be made by the Investigator to follow-up participants who withdraw from the study.

Participants may have a temporary interruption to their study intervention for management of toxicities.

Participants may be prematurely discontinued from the study intervention for any of the following reasons:

- Adverse event / Serious adverse event
- Protocol deviation
- Intolerability of injections
- Participant lost to follow-up
- Participant or Investigator non-compliance;
- Termination of the study by the Sponsor
- At the request of the participant, Investigator, GSK or ViiV Healthcare;
- The participant requires concurrent prohibited medications during the course of the study. The participant may remain in the study if in the opinion of the Investigator and the medical monitor; such medication will not interfere with the conduct or interpretation of the study or compromise the safety of the participant.

Participants must be discontinued from study intervention for any of the following reasons:

- Virologic withdrawal criteria as specified in Section 7.1.3 are met;
- Participant requires substitution of ART;
- Participant requires substitution or dose reduction of CAB LA, RPV LA (oral bridging supply and potential for a second loading dose may be permissible following discussion with the Medical Monitor) and oral DTG + RPV.
- Liver toxicity where stopping criteria are met and no compelling alternate cause is identified (see Section 7.1.1);

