#### 7.1.4. Strategy for Intercurrent (Post-treatment selection) Events

As defined by the Snapshot algorithm, HIV-1 RNA  $\geq$  50 c/mL is determined by the last available HIV-1 RNA measurement while the participant is on treatment within the analysis visit window of interest.

Participants without on-treatment HIV-1 RNA data for the visit of interest and who discontinue treatment for reasons not related to adverse event while having HIV-1 RNA  $\geq$  50 c/mL at time of discontinuation or who change study treatment not permitted per protocol before the analysis window are classified as having HIV-1 RNA  $\geq$  50 c/mL.

Full details of the snapshot algorithm are defined in Appendix 9: Snapshot Algorithm Details.

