#### Discontinued for Other Reasons:

- Only patients who have achieved virologic suppression can be counted as *Discontinued* for Other Reasons.
- If a patient discontinues the study before the time window because of *lack of efficacy* then the patient should be included in the HIV-RNA greater than or equal to 50 row and not in the Discontinued for Other Reasons row.
- If a patient discontinues because of subject withdrew consent and his or her HIV-1 RNA
  result at the time of discontinuation was equal to or above 50 copies/mL, then he or she
  should be categorized as HIV-RNA greater than or equal to 50 and NOT as
  Discontinued for Other Reasons.
- If a patient discontinued because of *Lost to Follow-Up* and the last HIV-RNA result was 49 copies/mL, then the patient can be categorized as Discontinued for Other Reasons.
- If patients changed background treatment *not permitted by protocol* they should be captured in the HIV-RNA greater than or equal to 50 copies/mL row.

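### SAP Appendix 9 exempts dropping a component from the Snapshot change-in-therapy conditions, so a participant left on one of two drugs gets opposite primary-endpoint classifications

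*SAP*

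**What the plan says.** SAP Appendix 9 (12.9) defines the Snapshot classification behind the primary endpoint, the proportion with HIV-1 RNA ≥50 c/mL at Month 12. Its detailed steps begin with an exemption: "Please note that the following scenarios will NOT be penalized Per Snapshot algorithm". The item listed is "Dose reduction, dropping a component, or change in formulation", illustrated by a move from Tivicay + Kivexa to Triumeq. These cases are to be left out of Conditions 1 to 4.

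The starred note in the same appendix reads the other way: "since changes in ART are not permitted in this protocol, all such subjects who change ART during the maintenance phase" and before an analysis timepoint are counted as ≥50 c/mL. It names one exception: "Participants with protocol permitted oral bridging treatment will not be considered" failures on that ground. Two further places agree with the note:

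- The guidance examples at the end of the appendix say that patients with a non-permitted change of background treatment should be "captured in the HIV-RNA greater than or equal to 50 copies/mL row".
- SAP 7.1.4 says that participants "who change study treatment not permitted per protocol before the analysis window are classified as having HIV-1 RNA" ≥50 c/mL.

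The protocol does not plan for one-drug or reduced-dose treatment. Section 6.7 states: "No dose reductions, modifications, or changes in the frequency of any components of each regimen will be allowed during the study", apart from what the protocol allows or the Medical Monitor directly approves. Section 7 lists as a reason for mandatory discontinuation: "Participant requires substitution or dose reduction of CAB LA, RPV LA", with a parenthesis that leaves room for oral bridging and a second loading dose. Section 6.8 has all antiretrovirals held when one is held for toxicity. Section 7.1.5 bars ART changes before virologic failure outside the planned regimens. Section 8.6.1 bars toxicity-related dose reductions.

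**The concern.** The two study regimens are CAB LA + RPV LA and DTG + RPV. Nothing sits behind them as background therapy, so dropping a component leaves a single drug. The exemption stops that event from being scored as a change in therapy, while the note beside it says that a change of ART before the timepoint is a failure. A programmer cannot follow both.

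At stake is whether someone suppressed on one drug is reported as a success of the two-drug regimen. The endpoint is expected to rest on very few failures (Protocol Table 6 considers 2% to 4%), so a single classification is visible in the result.

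**Working it through.** **Does the exemption change anything?** The instruction to leave these cases out of Conditions 1 to 4 has an effect only if those conditions would otherwise catch them. Conditions 2 and 4 are marked as not applicable to this study, so the comparison is between Conditions 1 and 3 (non-permitted change before or during the window) and Condition 5 (everyone else). SAP 12.4.2, note b, treats all assessments as on-treatment unless study treatment was permanently discontinued. A participant who continues on one drug therefore still supplies values to Condition 5.

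| One drug dropped, participant still on study | Processed under Conditions 1 and 3 | Exempted, so Condition 5 |
|---|---|---|
| Before the window; last in-window value <50 | ≥50 (Condition 1) | <50 |
| Before the window; last in-window value ≥50 | ≥50 (Condition 1) | ≥50 |
| Before the window; no in-window value | ≥50 (Condition 1) | No virologic data |
| During the window; ≥50 up to the change, <50 later | ≥50 (Condition 3) | <50 |
| During the window; no value up to the change, <50 later | ≥50 (Condition 3) | <50 |
| During the window; <50 up to the change, ≥50 later | <50 (Condition 3) | ≥50 |

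For a drug dropped before the window, the exemption can only lower the failure count. Measured against the note, which scores every change before the timepoint as ≥50 c/mL, it can also only lower it. The last row is the one place where the difference from Condition 3 runs the other way: Condition 3 stops at the date of change, and Condition 5 uses the last value in the window.

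**How far the supporting text reaches.** The note speaks of changing ART and does not name dose reduction. The sentence in SAP 7.1.4 opens with participants who lack on-treatment data for the visit. Read strictly, it may not reach someone with an in-window value. The firm conflict is between the exemption and the appendix's own note and Condition 1.

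**Scale.** The inputs are N = 100, an observed 3%, and the two-sided 95% normal-approximation limit (Protocol 10.2.1, Table 6). The upper limit is p + 1.96 × √(p(1 − p)/n).

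- Table 6 check: 0.03 + 1.96 × √(0.03 × 0.97/100) = 0.0634, against the stated 6.3%. All nine cells of the table reproduce to one decimal.
- One more failure: 0.04 + 1.96 × √(0.04 × 0.96/100) = 0.0784, or 7.8%.
- Two or three more: 5/100 gives 9.3% and 6/100 gives 10.7%.
- Going from 3 to 4 failures at other sizes: 7.0% to 8.7% at N = 90, and 5.8% to 7.1% at N = 110.
- Exact (Clopper-Pearson) limits for 3/100 and 4/100: 8.5% and 9.9%.

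The 100 is total enrolment over both elected regimens, and SAP 7.1.2 reports the endpoint by treatment group. In a group of n participants, one person moves the rate by 1/n, which is more than one percentage point when n is below 100.

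**The case against.** The strongest reply is that the appendix gives a general rule with an express carve-out, and that dosing shortfalls are handled elsewhere. SAP 12.1.1 excludes from the per-protocol population those with at least 10% of on-treatment time under-dosed, giving a 2 mL injection in place of 3 mL as an example, and Table 2.02 repeats the Month 12 Snapshot in that population. Keeping dosing non-compliance as observed in ITT-E is a legitimate choice. A virology-first algorithm should not turn a suppressed participant with one short injection into a failure.

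For dose reduction this largely stands. A reader might infer that the appendix itself requires every dose reduction to be scored ≥50 c/mL. It does not: its note does not mention dose reduction, and Protocol 6.7 leaves room for modifications that the Medical Monitor approves. What remains is a mismatch between an exemption for dose reduction and a protocol that otherwise bars it.

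For dropping a component the reply is weaker. Giving up one of two drugs is hard to read as anything but a change of ART, and the note excepts only oral bridging. Criterion 03 of SAP 12.1.1 also keeps permanent changes of ART regimen as ≥50 c/mL in the per-protocol Snapshot, so the SAP elsewhere treats a lasting regimen change as failure.

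It is also fair that the affected group should be nearly empty. DTG + RPV is one fixed-dose tablet, and Protocol 6.8 and 7 direct such cases towards holding all drugs or discontinuing. A reader might suppose that the exemption was carried over from another trial, since its example names products that are not study regimens. The SAP does not state its origin, and the point does not depend on it.

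**Conclusion.** The conflict over dropping a component is real and lies in the primary-endpoint rule. It should be resolved before database freeze. It does not show that the result will be materially biased. The exemption removes only the automatic failure for a change, a last in-window value ≥50 c/mL still fails under Condition 5, and the protocol makes the situation unlikely. The number affected is probably very small and cannot be estimated from the documents, so the shift from 6.3% to 7.8% is an illustration for one assumed participant out of 100. The study is descriptive with no hypothesis test, so no decision threshold is crossed. The dose-reduction wording needs reconciling with the protocol, and no more than that.

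**What to change.** In SAP Appendix 9:

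1. Remove dropping a component from the exemption, so that sustained use of one drug outside permitted oral bridging is processed under Conditions 1 and 3. Keep the exemption for formulation changes with identical ingredients, and keep the oral-bridging exception.
2. Reconcile the dose-reduction exemption with Protocol 6.7, 7 and 8.6.1. State that isolated dosing errors stay as observed in ITT-E and are handled by the per-protocol criteria of SAP 12.1.1. State how modifications approved by the Medical Monitor are classed.
3. Align the wording of SAP 7.1.4 with the result, making clear whether its rule on non-permitted changes also covers participants with in-window data.

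The first item is a one-sentence edit, and the others are short clarifications. None needs new data or sets a clinical rule. The cost is that the reported failure rate may become slightly less favourable.

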6.7.1. Protocol Permitted Substitutions

6.7.1.1. Oral Bridging

In exceptional circumstances, to address pre-planned missed CAB LA + RPV LA dosing visits, in consultation with the medical monitor, Investigators may provide daily oral CAB 30 mg and RPV 25 mg as a short-term “bridging” strategy for participants who have begun CAB LA + RPV LA. In certain circumstances (e.g., prior to steady state dosing and following a >4 week oral bridge) repeating the loading doses of CAB IM and RPV IM may be required. Should a participant require “oral bridging”, sites must contact the study Medical Monitor for guidance with treatment and dosing strategies prior to a missed CAB LA + RPV LA dose.

Please refer to [Appendix 10](#) in Section 12.10 for study management information during the COVID-19 pandemic.

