The investigator should reach out to the medical monitor to confirm IM restart instructions, and to ensure the participant remains appropriate for resumption of IM dosing. If oral bridging with CAB/RPV is anticipated to continue for > 2 months, additional approval and guidance should be obtained from the medical monitor to continue with oral bridging therapy. Loading/Re-initiation doses of CAB + RPV IM may be required, depending on the length of oral bridging.

Oral bridging with Standard of Care Antiretroviral Therapy (SOC ART)

For participants impacted by COVID-19, where the participant is unable to receive IM injections, and oral CAB + RPV is not available for use, oral bridging with any commercially available, guideline-recommended, SOC ART regimen is permitted. The start date of oral bridging should be within the dosing window for the missed IM dosing visit. Please reach out to your study medical monitor for approval of SOC ART as oral bridging, in order to document the use of commercially available SOC ART within the study.

Participants who use oral SOC ART as short-term oral bridging as a result of COVID-19 will not be considered formally withdrawn insofar as they wish to continue on the study. Individuals who bridge with SOC ART will be permitted to return to IM dosing, on study, once the COVID-19 conditions permit resumption of site activities.

The investigator should reach out to the medical monitor to confirm IM restart instructions, and to ensure the participant remains appropriate for resumption of IM dosing. If oral bridging with SOC ART is anticipated to continue for > 2 months, additional approval and guidance should be obtained from the medical monitor to continue with oral bridging therapy. Loading/Re-initiation doses of CAB + RPV IM may be required, depending on the length of oral bridging.

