12.10.6. COVID-19 Specific Data Capture

12.10.6.1. Capturing COVID-19 Specific Protocol Deviations

In order to summarise the impact of COVID-19 in a systematic way and in line with regulatory authorities' recommendations, any study-level impact around COVID-19 will be documented as a protocol deviation. This will include the permissible actions summarized in this Appendix, which are taken to protect patient safety, including the use of CAB + RPV or SOC ART as oral bridging as well as missed visits and assessments as a result of logistical challenges resulting from COVID-19.

Although the conduct of remote visits and the continuity of antiretroviral therapy, via oral bridging, are being utilized to protect patient safety, these events fall outside of the intent of the original protocol design, may have an impact on data interpretation, and thus will be characterized as protocol deviations for the purposes of data summary and analysis.

Any protocol deviations resulting from COVID-19 will be clearly identified as such within the protocol deviation description and summarised separately.

Please refer to your study procedure manual for specific details on capturing protocol deviations as a result of COVID-19.

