#### 12.4.2. Treatment State

Within each treatment study phase (i.e. Maintenance and LTFU—based on assignment of study phase described in Section 12.4.1), only those assessments which occur within the ranges shown in Table 15 will be considered 'on-treatment' for the given phase. No treatment states will be assigned to medications.

Table 15 Treatment State within Study Phases

Study Phase a	Treatment State	Date Range
Screening	Pre-treatment	All assessments/events within the phase
Maintenance	On-treatment	CAB LA + RPV LA:
		Date ≤ max (Date of Last Oral Dose of
		CAB+RPV + 1, Date of Last Injection + 67)
		DTG + RPV:
		Date ≤ Last Oral Dose Date + 1
	Post-treatment	CAB LA + RPV LA:
		Date > max (Date of Last Oral Dose of
		CAB+RPV + 1, Date of Last Injection + 67)
		DTG + RPV:
		Date > Last Oral Dose Date + 1
Long-Term	On-treatment	Date ≤ min(LTFU ART start date, max(Last
Follow-up		Injection Date + 67, Last Oral dose Date + 1))
	Post-treatment	Date > min(LTFU ART start date, max(Last
		Injection Date + 67, Last Oral dose Date + 1))

- Treatment State is determined after data has been assigned to the study phases as defined in Section 12.4.1
- b. Last injection and/or last oral dose of CAB+RPV are only applied to subjects who permanently discontinue from study treatment. The assessments for participants who did not permanently discontinue the study treatment will be considered 'On-treatment'
- c. Date = Assessment/Start Date.

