#### **Treatment Start Date**

Treatment start date is defined for the Maintenance Phase as follows:

- For subjects who were on CAB LA + RPV LA, this is the date of the first injection dose entered onto the IP exposure eCRF form.
- For subjects who were on oral DTG + RPV, this is the date of the first oral dose entered onto the IP exposure eCRF form.

For the long-term follow-up phase (only for CAB LA + RPV LA arm):

- If a participant is still on study treatment, or permanently discontinued the study treatment and did not have any previous injections, treatment start date is missing.
- If a participant permanently discontinued the study treatment and had at least one injection, treatment start date is the date of first HAART treatment after the last dose of study treatment (oral or injection).

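### The protocol now permits COVID-19 bridging with standard-of-care ART, but the SAP's Snapshot rules do not provide for it, and their two possible readings give different results, neither of which isolates the injectable regimen

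*SAP*

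**What the plan says.** **Protocol.** Section 6.7.1.1 describes bridging with the study drugs in oral form: "Investigators may provide daily oral CAB 30 mg and RPV 25 mg as a short-term" bridge. Section 12.10.3 (Appendix 10) adds a further option when COVID-19 prevents injections and oral CAB + RPV is not available: "oral bridging with any commercially available, guideline-recommended, SOC ART regimen is permitted". It may run beyond 2 months with further medical monitor approval. These participants "will not be considered formally withdrawn insofar as they wish to continue on the study" and may return to injections. Section 12.10.6.1 says that such events "will be characterized as protocol deviations for the purposes of data summary and analysis".

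**SAP.** Section 2.1 names protocol amendment 1 (22 June 2018) as its reference. The rules that bear on SOC bridging are:

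- Section 12.4.2, Table 15, note b: "The assessments for participants who did not permanently discontinue the study treatment will be considered 'On-treatment". The cut-off at last injection + 67 days applies only after permanent discontinuation.
- Sections 12.4.1 and 12.6.1: the Maintenance phase for viral load ends at the LTFU ART start. After permanent discontinuation, "treatment start date is the date of first HAART treatment after the last dose of study treatment (oral or injection".
- Section 12.9, note on changes in ART: its first sentence treats any change of ART before an analysis timepoint as ≥50 c/mL. Its second sentence is the exemption: "Participants with protocol permitted oral bridging treatment will not be considered 'HIV-1 RNA ≥ 50 c/mL' due to 'change in ART". No regimen is named.
- Section 12.9, steps 2 and 4, for permitted changes: step 2 asks whether "the latest on-treatment VL prior to/on the date of change is ≥ 50 c/m (NA to this study"), and step 4 is marked not applicable in the same way.

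**The concern.** The Snapshot outcome for the Q2M arm is meant to describe CAB LA + RPV LA. A viral load taken while a participant is on another complete regimen says little about whether the injections maintain suppression. The SAP does not say whether such a value is on-treatment by intention, or whether SOC ART is permitted bridging or a non-permitted change.

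The choice matters because the planned failure rate is low. Protocol Table 6 considers 2% to 4%, which is 2 to 4 participants in 100, so a handful of bridgers could change the reported rate materially. In an open-label study the rule should be fixed before anyone sees how many participants it moves, and in which direction.

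**Working it through.** **1. The plan's own figure.** Protocol Table 6 uses the normal approximation, p + 1.96 × √(p(1 − p)/n). With p = 0.03 and n = 100: 0.03 + 1.96 × 0.01706 = 0.0634, the stated 6.3%. All nine cells of the table reproduce to one decimal. That figure is not in dispute.

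**2. Path of a Q2M participant on SOC ART who has not permanently discontinued.**

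- Table 13: there is no LTFU ART start date, so the viral load stays in Maintenance.
- Table 15, note b: it is on-treatment.
- *Reading A, SOC ART is permitted oral bridging.* Steps 1 and 3 do not apply, and steps 2 and 4 are switched off. Step 5.1 takes the last viral load in the window, so <50 c/mL on SOC ART is scored <50. A participant who was ≥50 at the switch and re-suppressed on SOC ART is also scored <50.
- *Reading B, SOC ART is a non-permitted change.* A change before the window is scored ≥50 by step 1, whatever the viral load. For a change during the window, step 3 uses the last viral load in the window up to the change, and gives ≥50 if there is none.

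**3. Path of a bridger who then permanently discontinues without returning to study drug.** The SOC ART start is the first HAART after the last study dose, so it becomes the LTFU ART start and closes Maintenance. Later viral loads on SOC ART leave the Snapshot. The same kind of measurement is therefore kept or dropped according to what the participant does afterwards.

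**4. Size.** Assumptions: 100 Q2M participants, 3 other failures, and k bridgers who switched before the window, were suppressed at the switch and are <50 c/mL on SOC ART in the window. The documents do not give k.

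- A: ≥50 = 3/100; <50 = (100 − 3)/100.
- B: ≥50 = (3 + k)/100; <50 = (97 − k)/100.
- C, viral loads on SOC ART off-treatment, hence no virologic data: ≥50 = 3/100; <50 = (97 − k)/100.

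| k | A: ≥50 / <50 | B: ≥50 (upper 95% limit) / <50 | C: ≥50 / <50 |
|---|---|---|---|
| 1 | 3% / 97% | 4% (7.8%) / 96% | 3% / 96% |
| 2 | 3% / 97% | 5% (9.3%) / 95% | 3% / 95% |
| 5 | 3% / 97% | 8% (13.3%) / 92% | 3% / 92% |
| 10 | 3% / 97% | 13% (19.6%) / 87% | 3% / 87% |

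For k = 5 under B: 0.08 + 1.96 × √(0.08 × 0.92/100) = 0.08 + 1.96 × 0.02713 = 0.133. For suppressed bridgers, C differs from A only in the <50 endpoint.

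If 1 of the 5 had been ≥50 at the switch, A would still give 3% and 97%. With steps 2 and 4 active, and SOC viral loads off-treatment, the result would be (3 + 1)/100 = 4% and (100 − 3 − 5)/100 = 92%. The protocol's figure of about 100 covers both arms, so each Q2M participant may weigh somewhat more than 1 point.

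**5. Which analyses are exposed.** Protocol Appendix 10 dates the memo to investigators to 18 March 2020.

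- *Month 26.* The default Snapshot window opens on Study Day 721 (SAP Table 8). The original protocol is dated 16 May 2018, and 720 days later is 5 May 2020. The default window therefore falls after the memo for everyone.
- *Month 12.* The window closes on Study Day 375. It reaches 18 March 2020 only for a participant whose Day 1 was on or after 10 March 2019 (374 days earlier). Enrolment dates are not given.

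**The case against.** The strongest reply is that this is a version lag with limited reach. The latest date visible in the SAP is 28 January 2020, before the memo. SOC ART is the last resort: COVID-19 only, oral CAB + RPV unavailable, and medical monitor approval required. The study is descriptive, with no hypothesis test. SAP 12.12.3 says that the Month 26 and end-of-study outputs might not be produced, although Section 3.2 says that an end-of-study analysis will be conducted. Concomitant ART is already listed, and COVID-19 deviations are to be summarised separately. All of this stands and bears on severity. It does not supply the missing rule. Nor does per-protocol exclusion 03, because it spares ART allowed by the study.

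A reader might also infer more than the documents support:

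- *That every viral load on SOC ART counts as on-treatment.* It does not after permanent discontinuation (step 3 of the working).
- *That the bias favours the regimen.* That follows from reading A only. The SAP cites amendment 1, and its dosing rules mention only oral CAB + RPV, so reading B is equally open and runs the other way. Nor does reading B fail every bridger, given step 3 of the algorithm.
- *That the not-applicable marking is what turns suppressed bridgers into successes.* Steps 2 and 4 require a viral load ≥50 at the change. Activating them alone would still send suppressed bridgers to step 5.1.
- *That failures are erased.* Confirmed virologic failures must discontinue study intervention (Protocol 7.1.5.3). An earlier value ≥50 can still count in its own visit window, and all HIV-1 RNA data are listed for anyone ≥50 during Maintenance. Within one window, taking the last value is how Snapshot works. What remains is the unconfirmed or low-level viraemic participant who bridges and re-suppresses.

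**Conclusion.** The concern holds as an unresolved classification, not as a demonstrated bias in one direction. Applied to the current protocol, the SAP either credits suppression on another regimen to CAB LA + RPV LA or fails participants who were suppressed throughout, and it does not say which. With 3 other failures in 100 and an assumed 5 suppressed bridgers, the primary-type ≥50 result is 3% (upper limit 6.3%) or 8% (13.3%), and the <50 result is 97% or 92%. The number bridged is an assumption.

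Month 26 and end-of-study Snapshot results, if produced, are exposed. Month 12 is exposed only for visits after 18 March 2020, so an effect on the primary endpoint is possible but not shown. This should be fixed; it does not by itself invalidate the primary analysis.

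**What to change.** Update SAP 12.4.2 and 12.9 to the current protocol:

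1. State that viral loads from the start of SOC ART until injections resume are not on-treatment for Snapshot, whether or not injections later resume. This extends the cut-off at ART start that the SAP already uses for participants who discontinue.
2. Limit the exemption in the change-in-ART note to oral CAB + RPV bridging.
3. Treat SOC bridging as a permitted change and make steps 2 and 4 active: a last on-treatment viral load ≥50 c/mL before the change gives HIV-1 RNA ≥50. As written, step 2 would hold such a participant at ≥50 at later visits even after injections resume, so the SAP should say whether that is intended.
4. Place other SOC bridgers with no on-treatment value in the window under the existing no-virologic-data response.
5. List the SOC-bridged participants and report the alternative classification as a sensitivity analysis.

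The cost is SAP text and programming on ART data that are already collected. A few participants may move from <50 to no virologic data, so the reported success rate may be slightly lower. Other rules could be defended; what matters is that one is stated before the analysis and the other is shown beside it.
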